#### RELEVANT HABITS

12. History of regular alcohol consumption within 3 months of the study defined as:

Alcohol will be allowed but limited to an average weekly intake of <21 units for males or <14 units for females).

13. Direct exposure to UV light (e.g. sunbathing) to the testing areas within 2 weeks of study entry.

#### CONTRAINdicATIONS

14. History of sensitivity to any of the study medications, or components thereof or a history of drug or other allergy that, in the opinion of the investigator or Medical Monitor, contraindicates their participation (refer to the Investigator Brochure for a list of excipients).

#### DIAGNOSTIC ASSESSMENTS AND OTHER CRITERIA

15. Presence of hepatitis B surface antigen (HBsAg), positive hepatitis C antibody test result at screening or within 3 months prior to first dose of study treatment.

16. A positive HIV test at screening

17. A positive pre-study drug screen.

18. Where participation in the study would result in donation of blood or blood products in excess of 450 ml within 3 months.

19. The subject has participated in a clinical trial and has received an investigational product within the following time period prior to the first dosing day in the current

study: 30 days, 5 half-lives or twice the duration of the biological effect of the investigational product (whichever is longer).
20. Exposure to more than 4 investigational medicinal products within 12 months prior to the first dosing day.
Country Specific Exclusion criteria wording for Germany:
21. Subjects that are employees of either GlaxoSmithKline (sponsor) or one of the study centres (investigators).
22. Subjects who live in detention on court order or on regulatory action, see §40 subsection 1 sentence 3 no. 4 AMG. (Arzneimittelgesetz).

#### CONCOMITANT MEDICATIONS

23. Oral Prednisolone

- Greater than 7.5 mg by mouth daily.
- Any increase in dose from screening to Day 28

24. Hydroxychloroquine

- Greater than 400mg oral daily.
- Any increase in dose from screening to Day 28.

25. Photosensitizing drugs within 5 half-lives prior to the photoprovocation visit.

### 5.3. Screening/Baseline Failures

Screen failures are defined as subjects who consent to participate in the clinical trial but are never subsequently randomised. In order to ensure transparent reporting of screen failure subjects, meet the Consolidated Standards of Reporting Trials (CONSORT) publishing requirements, and respond to queries from Regulatory authorities, a minimal set of screen failure information is required including Demography, Screen Failure details, Eligibility Criteria, and Serious Adverse Events (see Section 7.4.1.6).

Screening assessments that yield initially aberrant results (e.g. safety laboratory samples) may be repeated by the investigator based on their judgement. Subject re-screening is allowed up to a maximum of 2 times.

## 5.4. Withdrawal/Stopping Criteria

### WITHDRAWAL CRITERIA(Specific for Group A ONLY)

1. A subject will be withdrawn from the study, if they demonstrate an excessive or adverse reaction to the photoprovocation, as judged by the Investigator after discussion with the medical monitor.

The following actions must be taken in relation to a subject who fails to attend the clinic for a required study visit:

- The site must attempt to contact the subject and re-schedule the missed visit as soon as possible.
- The site must counsel the subject on the importance of maintaining the assigned visit schedule and ascertain whether or not the subject wishes to and/or should continue in the study. In case a subject withdraws from study they should be encouraged to continue contraception for 28 days.
- In cases where the subject is deemed 'lost to follow up', the investigator or designee must make every effort to regain contact with the subject (where possible, 3 telephone calls and if necessary a certified letter to the subject's last known mailing address or local equivalent methods). These contact attempts should be documented in the subject's medical record.
- Should the subject continue to be unreachable, only then will he/she be considered to have withdrawn from the study with a primary reason of "Lost to Follow-up".

A subject may withdraw from study treatment at any time at his/her own request, or may be withdrawn at any time at the discretion of the investigator for safety, behavioural or administrative reasons. If a subject withdraws from the study, he/she may request destruction of any samples taken, and the investigator must document this in the site study records.

At the time a subject withdraws, every effort should be made to conduct assessments stipulated at the follow-up visit, as per the time & events tables, Section 7.1.

If subjects prematurely discontinue the study, additional replacement subjects may be enrolled at the discretion of the Sponsor in consultation with the investigator.

### 5.4.1. Safety Related Stopping Criteria for an Individual Subject

A female subject will be withdrawn from the study if a positive pregnancy test is obtained during the study.

A subject may be withdrawn from the study if they present dose limiting toxicity.

Toxicity is defined as dose-limiting toxicity if it meets the following criteria:

- Occurs within 24 hours after any dose.
- and is considered by the Investigator to be possibly or probably related to treatment

- and, for AE or laboratory abnormality, is severe
- and, for tolerability,
  - is of Grade 3 or higher for “dermal response scoring (i)”, and
  - is Grade C, F, G, or H according to the “other effects scoring (ii)” (Section [5.4.2](#) below)
- and for Thyroid function – TSH to remain within the normal range at Day 14

If dose limiting toxicity is observed in an individual, the investigator or designee may use their medical judgment to stop dosing the individual subject, and is required to immediately inform the GSK medical monitor or designee. They will then decide whether it is necessary for the Safety Review Team (SRT: See Section [10.8](#)) to be convened immediately for review of the data and decision on dose adjustment or withdrawal of the individual subject.

The SRT will:

- Evaluate and confirm potential dose-limiting toxicities both as data is generated (so-called ‘in-stream review’), and at any point during the study when a bulk of data review is determined necessary (e.g. this may be conducted once all subjects in group A complete all study visits, or at any other point during study conduct).
- Pause enrolment and/or request safety-related changes to the trial protocol.

At a minimum (but not limited to), the following data-sets will be reviewed by the SRT:

- Clinical laboratory assessments
- Vital signs
- Adverse (& serious adverse) Events
- Local tolerability assessments

Additional data-sets not listed above may also be reviewed as deemed appropriate by the SRT.

A subject may be withdrawn from the study if they present a Serious Adverse Event (SAE), regardless of its severity, and reasonably attributable in the opinion of the investigator to dosing with GSK2646264.

A subject will be withdrawn if they require concomitant medications as specified and listed in Section [5.2](#).

In the presence of any of the above events, every effort will be made to take a blood sample at the time of the event for pharmacokinetics analysis.

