Thyroid follicular epithelial hypertrophy	
Minimal thyroid follicular epithelial hypertrophy was observed in all doses following iv administration of GSK2646264 in rats for 4 weeks. Thyroid hormones (TSH, T3 and T4) at a single timepoint 12 hours post last dose were within normal range.
 
No similar changes were seen following dermal administration of GSK2646264 in rats for 4 weeks which resulted in similar AUC values but lower Cmax values.
 
The ongoing clinical study has not identified clinical signs or symptoms of thyroid dysfunction to date.
	
The risk of thyroid effect in this study is considered not to be significant.
 
Subjects with history of Graves' disease, thyroid cancer, or abnormal thyroid function as measured by TSH, free T4 and free T3, will be excluded from this study.
 
Monitoring will be based on signs and symptoms, and serum markers of thyroid function will be measured in patients as outlined in Section 7.1

Potential Risk of Clinical Significance	Summary of Data/Rationale for Risk	Mitigation Strategy
Hypersensitivity to formulation	
Dose related dermal findings in the rat were limited to observations of transient erythema and eschar at 1 and 3% (w/w). Desquamation was observed in one control and one treated animal at 3% (w/w). There were no histopathological correlates to these observations. Erythema was also a transient observation in the minipig but occurred with both vehicle and test article formulations without relationship to GSK2646264 (mesylate salt) dose strength and without histopathological correlate.
 
There may be potential for hypersensitivity reactions from the procedures used in the study or if subjects are allergic to ingredients in the study medications.
 
The ongoing FTIH study has not identified any significant safety concerns to date, as assessed by adverse events.
	
Subjects will be excluded from the study if they are allergic to any ingredient of the study medications.
 
Subjects will undergo regular medical assessment and instructed on what action to take in the event of an allergic reaction, see Section 7.1.

Study Procedures		

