## 5.1. Inclusion Criteria

A subject will be eligible for inclusion in this study only if all of the following criteria apply:

AGE
1. Between 18 and 70 years of age inclusive, at the time of signing the informed consent.
TYPE OF SUBJECT AND DIAGNOSIS INCLUDING DISEASE SEVERITY
2. Subject values for the following parameters TSH, free T4, and free T3 within the normal range. 3. Subject has confirmed diagnosis of LET (group A only), subacute or chronic CLE as determined by the investigators.  A subject with a clinical abnormality or laboratory parameter(s) which is/are not specifically listed in the inclusion or exclusion criteria, outside the reference range for the population being studied may be included: only if the investigator in consultation with the Medical Monitor if required agree and document that the finding is unlikely to introduce additional risk factors and will not interfere with the study procedures.

WEIGHT
4. Body mass index (BMI) $\geq 19\text{kg/m}^2$ (inclusive)

SEX
5. Male OR Female
Females:
a. Non-reproductive potential defined as:
• Pre-menopausal females with one of the following:
• Documented tubal ligation
• Documented hysteroscopic tubal occlusion procedure with follow-up confirmation of bilateral tubal occlusion
• Hysterectomy
• Documented Bilateral Oophorectomy
• Postmenopausal defined as 12 months of spontaneous amenorrhea. In questionable cases a blood sample with simultaneous follicle stimulating hormone (FSH) and estradiol levels consistent with menopause (refer to laboratory reference ranges for confirmatory levels). Females on hormone replacement therapy (HRT) and whose menopausal status is in doubt will be

required to use one of the highly effective contraception methods if they wish to continue their HRT during the study. Otherwise, they must discontinue HRT to allow confirmation of post-menopausal status prior to study enrolment.

b. Reproductive potential and agrees to follow one of the options listed in the Modified List of Highly Effective Methods for Avoiding Pregnancy in Females of Reproductive Potential (FRP) (see Section 12.4) from 28 days prior to the first dose of study medication and until 12 days after the last dose of study medication and completion of the follow-up visit.

The investigator is responsible for ensuring that subjects understand how to properly use these methods of contraception.

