## 7.1. Time and Events Tables

### 7.1.1. Group A

Procedure	Screening (up to Day - 28)	Day -15	Day -14	Day - 13 to - 1	Day 1	Day 2 to Day 13	Day 14	Day 15 to Day 20	Day 21 to Day 27	Day 28	Day 29 to 42	Follow- up a	a All procedures listed to also be conducted if a subject decides to prematurely withdraw/discontinue
Informed Consent	X												
Inc/Exc criteria assessment	X												
Demography	X												
Pregnancy Test (women)	X				X		X					X	Pregnancy testing to be performed at Screening, on Day 1 (pre-dose), Day 14 (pre-dose) and once during follow-up, with day recorded
TSH, free T4, free T3	X				X		X					X	
Vital Signs	X	X			X		X			X			
Safety Lab Samples (clin chem, haematol, Urinalysis)	X	X		X	X		X			X		X	On days of dosing samples should be taken predose.  Sample timepoints during the Day-13 to Day-1 period are as follows: – once weekly during visits to assess PV lesion development
Full Physical Exam	X											X	

Procedure	Screening (up to Day - 28)	Day -15	Day -14	Day - 13 to - 1	Day 1	Day 2 to Day 13	Day 14	Day 15 to Day 20	Day 21 to Day 27	Day 28	Day 29 to 42	Follow- up a	a All procedures listed to also be conducted if a subject decides to prematurely withdraw/discontinue
Brief Physical Exam				X									Assessment to be performed pre-dose  Sample timepoints during the Day-13 to Day-1 period are as follows: – once weekly during visits to assess PV lesion development
12-lead ECG	X				X		X					X	On days of dosing assessments should be performed pre-dose
SLE clinical assessment	X				X					X		X	On days of dosing assessment as defined by the investigator to be performed pre-dose .
ANA, anti-dsDNA, anti-Ro and anti-La antibodies, HIV, Hep B, Hep C, FSH, Drug screen	X												
Skin Biopsies					X b					X b			b Day 1 biopsies will be taken pre-dose. Day 28 biopsies will be taken 4 hours post-dose
UV threshold testing		X											
Photoprovocation				X c, d									Performed 24 hours after UV threshold testing. c PV occurs once every 24 hours for 3 days on Day-14, Day-13 & Day-12. d If PV induced lesions appear at all 3 sites after Day -14 or Day -13, PV treatment can be stopped early

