## 7.1.3. Group B

Procedure	Screening (up to Day -28)	Day -5 to -3	Day 1	Day 2 to Day 13	Day 14	Day 15 to Day 20	Day 21 to Day 27	Day 28	Day 29 to 42	Follow-up (between Day 43 to Day 56) a	All procedures listed to also be conducted if a subject decides to prematurely withdraw/discontinue
Informed Consent	X										
Inc/Exc criteria assessment	X										
Demography	X										
Pregnancy Test (women)	X		X		X				X	Pregnancy testing to be performed at Screening, on Day 1 (pre-dose), Day 14 (pre-dose) and once during follow-up, with day recorded	
TSH, free T4, freeT3	X		X		X				X		
Vital Signs	X	X			X			X			
Safety Lab Samples (clin chem ,haematol, Urinalysis)	X	X	X		X			X	X	On days of dosing samples should be taken predose	
Full Physical Exam	X								X		
Brief Physical Exam			X							Assessment to be performed pre-dose	
12-lead ECG	X		X		X				X	On days of dosing assessments should be performed predose	
SLE clinical assessment	X		X					X	X	On days of dosing assessment as defined by the investigator to be performed pre-dose .	
ANA, anti-dsDNA antibodies, anti-Ro and anti-La antibodies, HIV, Hep B, Hep C, FSH, Drug screen	X										
Lesion selection		X								Refer to Section 4.1 and	

Procedure	Screening (up to Day -28)	Day -5 to -3	Day 1	Day 2 to Day 13	Day 14	Day 15 to Day 20	Day 21 to Day 27	Day 28	Day 29 to 42	Follow-up (between Day 43 to Day 56) a	a All procedures listed to also be conducted if a subject decides to prematurely withdraw/discontinue
											Section 6.1
Skin Biopsies		X b						X b			b 2 to 4 days healing time will be allowed prior to randomisation and the first dose. Day 28 biopsies will be taken 4 hours post-dose
Clinical score			X		X			X			
Local tolerability Assessment			X	X	X	X	X	X	X		Assessments to be performed pre-dose and up to one hour following dosing on days of dosing
Dosing			X	X	X	X	X	X			Once daily
Randomisation			X								Pre-dose

Procedure	Screening (up to Day -28)	Day -5 to -3	Day 1	Day 2 to Day 13	Day 14	Day 15 to Day 20	Day 21 to Day 27	Day 28	Day 29 to 42	Follow-up (between Day 43 to Day 56) a	a All procedures listed to also be conducted if a subject decides to prematurely withdraw/discontinue

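### The thyroid limb of the dose-limiting-toxicity rule in Protocol 5.4.1 is worded backwards: it lists a normal Day 14 TSH, not an abnormal one, as the criterion

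*Protocol*

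**What the plan says.** Protocol 5.4.1 introduces its list with "Toxicity is defined as dose-limiting toxicity if it meets the following criteria". The first two conditions concern timing (within a day of a dose) and the investigator's view that the finding is possibly or probably related to treatment. Limbs by type of finding follow: severity for adverse events and laboratory abnormalities, set grades for local tolerability, and, for thyroid function, "TSH to remain within the normal range at Day 14".

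Three other places bear on how that limb should be read.

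- Inclusion criterion 2 in Protocol 5.1 requires "Subject values for the following parameters TSH, free T4, and free T3 within the normal range".
- Protocol 4.6.1 discusses thyroid follicular hypertrophy seen in rats after intravenous dosing. It relies on signs and symptoms plus serum thyroid markers for monitoring, and concludes: "The risk of thyroid effect in this study is considered not to be significant".
- Protocol 5.4.3 uses the same definition at study level: dose-limiting toxicity in at least 2 subjects leads to reporting and discussion with the medical monitor and the Safety Review Team.

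**The concern.** A list of criteria for toxicity should describe the toxic state. Here the thyroid entry describes the state everyone hopes to see. A site applying 5.4.1 as written would find that a subject whose TSH had left the normal range on Day 14 does not meet the thyroid limb, while a subject whose TSH had stayed normal does.

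Two decisions hang on the definition: whether to stop dosing the individual, with immediate notice to the medical monitor, and the 2-subject count in 5.4.3. Laboratory tests are also part of the primary safety endpoint. A stopping rule should be usable as it stands, without the reader having to work out what was meant.

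**Working it through.** No figure in the plan depends on this wording, so the main check is a side-by-side reading.

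**Step 1. Direction of each limb in 5.4.1.**

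| Limb | State named | Direction |
|---|---|---|
| Adverse event or laboratory abnormality | severe | abnormal |
| Tolerability, dermal response | Grade 3 or higher | abnormal |
| Tolerability, other effects | C, F, G or H | abnormal |
| Thyroid function | TSH still normal at Day 14 | **normal** |

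Only the thyroid limb names the acceptable state.

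**Step 2. Intent.** Under 5.1 every eligible subject starts with normal TSH, free T4 and free T3. A TSH that *remains* normal is therefore an unchanged subject, which cannot be a toxicity. The intended trigger must be a TSH that leaves the range.

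**Step 3. Is the rule stated correctly elsewhere?** Sections 4.6.1, 5.4.3 and 10.8 and the Time and Events tables contain no TSH stopping criterion. The wording in 5.4.1 is the only one.

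**Step 4. Does another limb make it redundant?** Partly. A severe, related laboratory abnormality already counts. But 12.3.5 grades intensity by interference with everyday activities, so a symptom-free TSH outside the range would be hard to call severe. The thyroid limb has its own work to do once it points the right way.

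**Step 5. What the corrected limb would cost in chance flags.** Inputs: n = 15 (planned Group B size, Protocol 4.3; SAP 2.1 records that no Group A subject was randomised); one TSH per subject at Day 14 (Protocol 7.1.3); and a probability p that a TSH falls outside the range by chance. The documents give no value for p, so 1% to 5% is an assumption. Subjects are treated as independent.

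Expected flags = 15p: 15 × 0.01 = 0.15, and 15 × 0.05 = 0.75.

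P(2 or more flag) = 1 − (1 − p)^15 − 15p(1 − p)^14

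- p = 1%: 1 − 0.8601 − 0.1303 = 0.0096, about 1%
- p = 2.5%: 1 − 0.6840 − 0.2631 = 0.0529, about 5%
- p = 5%: 1 − 0.4633 − 0.3658 = 0.1709, about 17%

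These come before the relatedness judgement, which would remove some of the flags.

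**Step 6. Why the correction should stay at Day 14.** If the limb covered any on-treatment value and a Day 28 sample were added, the per-subject probability would become 1 − (1 − p)²: 1.99% at p = 1% and 9.75% at p = 5%. The same formula then gives 3.5% and 44% for 2 or more of 15. Widening the trigger would therefore be a change of policy, beyond correcting the wording.

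**The case against.** The strongest reply is that nobody would be misled. The lead-in requires a toxicity before any criterion is applied, a normal TSH is not one, and the word *remain* shows what was meant. Other safeguards also stand: clinically significant laboratory abnormalities are adverse events (12.3.1) and are to be repeated (7.4.7), the investigator may withdraw a subject at any time for safety (5.4), and the Safety Review Team looks at laboratory data as they accrue (5.4.1, 10.8). Withdrawal for dose-limiting toxicity is in any case optional. All of this stands, and it is why the effect is modest. It does not make the sentence right.

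A reader might infer more than the documents support in three ways.

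- *That subjects with a normal TSH would be stopped, or that thyroid toxicity would go unhandled.* The need for a toxicity and for relatedness prevents the first, and the safeguards above largely prevent the second.
- *That the missing Day 28 thyroid sample is an error.* The rows "TSH, free T4, free T3" (7.1.1) and "TSH, free T4, freeT3" (7.1.3) have no Day 28 draw, so 14 of the 28 doses (15 if the Day 14 sample is pre-dose) follow the last on-treatment value. But the 12-lead ECG, a named primary-endpoint measure, has the same schedule, and a follow-up thyroid sample exists. On the preclinical side, 4.6.1 reports "Thyroid hormones (TSH, T3 and T4) at a single timepoint 12 hours post last dose were within normal range" for the intravenous rat study, and "No similar changes were seen following dermal administration of GSK2646264 in rats for 4 weeks" for the dermal route. With the risk rated as it is, this is a defensible choice of schedule.
- *That the SAP leaves thyroid values out of the safety summary.* SAP Tables 2.5 and 2.6 name no analytes at all, so the absence of thyroid names shows little.

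**Conclusion.** The point holds as a wording error in an operative stopping rule. The thyroid limb in 5.4.1 states the opposite of what is evidently intended, and nothing else in the protocol states it correctly. That conclusion rests on the text alone.

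The importance is low. No sample size, estimate or analysis changes, and other routes to stopping or escalating remain open. The correction is worth making because it is cheap and because the definition also feeds the 2-subject discussion in 5.4.3. The figure of about 1% to 17% for 2 or more chance flags assumes 15 subjects, one Day 14 value each, independence and a 1% to 5% chance rate. It is a cost of the corrected rule and says nothing about whether the drug affects the thyroid.

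**What to change.** By protocol amendment, replace the thyroid bullet in 5.4.1 with: *or, for thyroid function, TSH outside the laboratory normal range at Day 14*. Lay out the list so that the timing and relatedness conditions plainly still apply to this limb, and leave the decision to withdraw discretionary. Keep Day 14 as the only time point, for the reason in Step 6.

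Costs:

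- An amendment for one line. The Note to File route in Section 7 covers changes to the timing or number of assessments prompted by newly available data; it does not cover rewording a stopping criterion.
- An occasional chance out-of-range TSH (0.15 to 0.75 expected among 15 subjects at the assumed rates). Each needs a relatedness judgement and could count towards the 5.4.3 discussion.

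Optionally, add TSH, free T4 and free T3 to the existing Day 28 safety blood draw as descriptive end-of-treatment data, kept outside the stopping rule. This needs no extra visit and about 15 more panels in Group B.

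The amendment helps only subjects still to be dosed. If dosing has ended, the study report should state how the limb was applied.
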